5.3.2 Cardiac MRI (Cohort 3)

MRI parameters will be measured at Baseline and then annually (every 48 weeks). Information concerning the MRI parameters will be added in a later version of the SAP. -

5.3.3 Fibre Regeneration [via Biopsy] (Cohorts 1 and 2)

Parameters will be measured from biopsies at Baseline and once post-dose, at either 24 weeks or 48 weeks. If a subject withdraws from the study prematurely they may also have a biopsy at the termination visit if they haven't already had their second biopsy.

At each time-point two samples will be taken.

Imputation will not be used for any missing data.

5.3.3.1 Developmental Heavy Chain Myosin (MHCd), Utrophin Expression and Fibre Diameter

Each sample will have, where possible, 3 sections assessed – different sections will be used for the Myosin and Utrophin assays. For each of these sections the following will be determined from the Myosin assay:

- Percentage of MHCd positive fibres (%MHCd positive)
- Percentage of fibres with 0, 1, 2 and 3 MHCd intensity
- MHCd heterogeneity score
- Fibre diameter - mean
- Fibre diameter – standard deviation

For the other sections the following will be determined from the Utrophin assay:

- Utrophin intensity – mean
- Utrophin intensity – standard deviation
- Utrophin intensity – mean, where utrophin expression is $\geq 75\%$ around the fibre
- Utrophin intensity – standard deviation, where utrophin expression is $\geq 75\%$ around the fibre
- Percentage of fibres with 0, 1, 2 and 3 Utrophin intensity
- Utrophin heterogeneity score

In addition to these parameters the percentage of Utrophin positive fibres (%UT positive) will be derived as (100 - % of fibres with 0 intensity).

The total number of fibres will also be recorded for both assays, but this is only information concerning the assay and isn't to assess treatment effect.

If there was a technical issue with the assay a value may be excluded from analyses. This exclusion has to be justified and documented by the pathologist/technician following their assessment of the stained image.

For each subject at each time-point the average will be calculated across sections for each sample and then the average will be calculated from the two sample averages. Changes from baseline will then be calculated from these averages.

5.3.3.2 % Necrosis/Inflammation, % Regeneration, %Fat and %Collagen

For each biopsy sample the % of necrosis / inflammation, % regeneration, %fat and %collagen will be estimated by semi-quantitative pathology assessment. Note that a single section stained with haematoxylin and eosin (H&E) will be taken from each sample to calculate % of necrosis / inflammation, % regeneration and %fat. A second section from each sample is stained with Masson's trichrome (MT) to calculate collagen.

Values from the two samples will be averaged. Changes from baseline will then be calculated for these averages.

5.3.4 Blood Biomarkers

Blood biomarkers (including creatine kinase and matrix metalloproteinase 9 [MMP9]) will be measured at Baseline and Weeks 4, 8, 12, 24, 36 and 48 during the first 48 weeks and then 6 monthly during the extension phase. Changes from baseline will be calculated. Imputation will not be used for any missing data.

Fibroblast growth factor 19 (FGF19) and 7 α -hydroxy-4-cholesten-3-one (C4) will be measured at screening, Day 1, end of study and Weeks 24 and 48. At Weeks 24 and 48 measurements will be taken pre-AM dose, 3h post-AM dose, pre-PM dose and 4h post-PM dose. On Day 1 only the pre and post- AM measurements will be taken.

5.4 Safety Assessments

5.4.1 Adverse Events (AE)

A treatment emergent AE (TEAE) includes any condition that: 1) was not present prior to study treatment, but appeared or reappeared following initiation of study treatment, or 2) was present prior to study treatment, but worsened during study treatment.

The duration of AEs will be derived as the AE end date (imputed date for incomplete AE end date) – AE onset date (imputed date for incomplete AE onset date) +1.

AEs leading to discontinuation of IMP are those with an action taken with study treatment on the AE eCRF page of “Drug Withdrawn”.

Treatment-related TEAEs are defined as those TEAEs where relationship to study treatment is either considered as ‘Possibly Related’ or ‘Probably Related’ by the Investigator. A missing value for relationship to treatment will be considered as ‘Related’ in summaries.

A missing assessment of severity will be considered as ‘severe’ in summaries.

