10.2. Patient Withdrawal

10.2.1. Patient Withdrawal from Investigational Medicinal Product

A patient will be withdrawn from treatment for any of the following reasons:

- Withdrawal of consent/assent to continue taking treatment
- The study Investigator or Sponsor, for any reason, decides the patient should be withdrawn from the treatment
- Adverse events, classed as possibly or probably related by the Investigator, which cannot be tolerated by the patient

If a patient is withdrawn from treatment where possible they should continue to attend all remaining study visits so that data can be collected. If patients will not assent or their parents/guardian will not consent to this then they should be withdrawn from the study.

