11. ADVERSE EVENTS AND SERIOUS ADVERSE EVENTS

11.1. Adverse Events

An AE is any untoward medical occurrence in a patient or clinical investigation patient administered a pharmaceutical product and which does not necessarily have a causal relationship with this treatment. An AE can therefore be any unfavourable and unintended sign (including an abnormal laboratory finding), symptom, or disease temporally associated with the use of a medicinal (investigational) product, whether or not related to the medicinal (investigational) product.

Adverse events will be recorded from the signing of the consent form until the end of the safety follow-up period or completion of the Extension Phase.

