4.0 Study Endpoints

4.1 Primary Endpoints

- Change from baseline to Weeks 12, 24, 36 and 48 in MRI leg muscle parameters (Cohorts 1 and 2)
- SMT C1100 and metabolite plasma concentrations at Weeks 1 (Days 1 and 7, as applicable (Cohorts 2 and 3 only)), 4, 8 (Cohorts 1 and 2 only), 12, 24, 36 and 48
- Safety data including:
 - Treatment emergent AEs

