9.1.1 Methods for Handling Dropouts and Missing Data

Imputation details concerning missing efficacy data where a subject has attended the relevant visit are discussed in **Section 5**. Where missing data is due to a missed visit values will not be imputed.

The imputation approaches for handling partial or missing start and/or end dates of AEs and concomitant medications are summarized in **Appendix 2**. Partial and missing AE or concomitant medication dates will be imputed with conservatism. Unless an AE is proven to occur prior to the first dose of the study drug, it will be considered to be a treatment-emergent adverse event (TEAE). Similarly, a medication with a missing stop date will be considered as concomitant medication unless there is obvious evidence that the stop date is prior to the first date of IMP treatment. If the day, or month and day, of the start date are not obviously before the date of first IMP treatment, then the start date will be imputed as the first day of the available month and or year, or the start date of IMP, whichever is later.

The imputed dates will be used to assess whether AEs should be considered to be treatment emergent, medications should be included in the safety summaries as prior and/or concomitant, and for the calculation of AE durations; however, the original partial/missing dates will be included in data listings.

Partial dates for age at diagnosis will also have the missing information imputed for the purposes of calculating the duration since diagnosis. The earliest date consistent with the information provided will be used.

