9.4.2 Prior and Concomitant Medications/Procedures

Prior/concomitant medications will be summarized by Anatomic Therapeutic Classification (ATC) class and preferred name. The analysis will be performed using the Safety population. Summaries will be presented for all medications and also specifically for steroids taken for DMD. The summaries will include the steroids taken for DMD by boys participating in the FOR-DMD study (recorded in DMD history page of eCRF); their data will be presented in a separate listing.

The numbers (%) of subjects using each medication will be displayed. Subjects taking more than one medication in the same ATC class or preferred name will be counted once for the number of subjects taking that preferred name.

Medications will be split into two groups, by clinical review; those taken specifically for the anaesthetics related to the biopsy procedure and all others. Separate listings will be generated for each group.

Separate concomitant medication summaries (all medications and steroid medications) will be generated for the first 24 weeks, first 48 weeks and for the whole study.

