9.8 Safety Analyses

9.8.1 Adverse Events

All safety analyses will be performed on the Safety population.

The listing of AEs will include the duration of the AE. It will be flagged if this is derived using imputed dates.

An overall summary will present the number (%) of subjects with:

- any TEAE

- any TEAE considered as related to study drug
- any serious TEAE
- Maximum intensity TEAE of none, mild, moderate, severe ; i.e. a subject with TEAEs at different intensities will be summarized at the most severe intensity
- any TEAE leading to study drug discontinuation
- any TEAE leading to death

The table will also include the total number of TEAEs reported and the total number of unique terms. For unique terms a preferred term will only be counted once within a subject.

Subject incidence of the following AEs will be tabulated by SOC (descending order of frequency) and PT (descending order of frequency):

- TEAEs
- treatment-related TEAEs
- maximum severity of TEAEs

Subject incidence of the following AEs will be tabulated by PT in descending order of frequency:

- TEAEs
- treatment-related AEs

Separate summaries will be generated for the first 24 weeks, first 48 weeks and for the whole study.

Serious TEAEs and TEAEs leading to discontinuation of study drug will be provided in by-subject listings.

Subjects will be counted only once within each SOC or PT. For tables categorized by severity, subjects with multiple events within a particular SOC or PT will be counted under the category of their most severe event for that SOC or PT.

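### The TEAE definition uses two different windows, so new events long after a boy stops drug can count in a primary endpoint, and the whole-study TEAE percentages ignore unequal follow-up

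*SAP*

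**What the plan says.** SAP 4.1 lists "Treatment emergent AEs" among the primary endpoints. SAP 5.4.1 defines them in two limbs:

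- Limb 1: a condition that "was not present prior to study treatment, but appeared or reappeared following initiation of study treatment".
- Limb 2: a condition that "was present prior to study treatment, but worsened during study treatment".

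SAP 9.1.1, which deals with partial and missing dates, tests an event only against the first dose: "Unless an AE is proven to occur prior to the first dose of the study drug, it will be considered" treatment-emergent.

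For boys who stop drug, Protocol 10.2.1 says: "If a patient is withdrawn from treatment where possible they should continue to attend all remaining study visits so that data can be collected". Protocol 4.2.2 likewise keeps a boy who is permanently stopped on the liver criteria in follow-up until the study ends. Protocol 11.1 records AEs "until the end of the safety follow-up period or completion of the Extension Phase", and Protocol 11.1.3 reports them up to the last study-related procedure. Neither end point depends on the boy's own last dose.

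On the tables, SAP 9.8.1 gives numbers and percentages of subjects and adds: "Separate summaries will be generated for the first 24 weeks, first 48 weeks and for the whole study". Under SAP 9.1 the denominator is the number of subjects in the population. SAP 7.0 puts the available extension data for Cohorts 1 and 2 into the main report. SAP 9.4.1 derives each boy's duration of exposure from his first and last dose dates, but no AE table uses it.

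**The concern.** The trial has no control arm, so the TEAE tables must be read on their own terms: what happened to boys while exposed to the drug. Two features blur that reading.

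First, limb 1 never closes. For a boy who stops drug but stays in the study, every new event up to his last contact enters a primary endpoint as treatment-emergent, however long he has been off drug. The definition also handles similar events differently, because off-drug worsening of an existing condition is left out.

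Second, a percentage of subjects with at least one event rises with time observed. In the whole-study table that time differs between boys, because the extension is optional and has no fixed length. Two groups at the same risk can then show different percentages.

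**Working it through.** The documents give no AE rate, discontinuation rate or derivation on this point, so there is no plan figure to reproduce. The check has three steps.

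**1. Does any other text close limb 1?**

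- SAP 9.1.1 gives a lower bound only (first dose).
- SAP 5.1, under the visit windows, includes data whatever the time since last dose and allows additional summaries without late assessments, case by case. It concerns assessments and sets no AE cut-off.
- Protocol 4.1.1 gives a 30-day safety follow-up after the initial Treatment Phase. This closes the window in practice for a boy who completes 48 weeks and leaves, but not for one who stops early and keeps attending.

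Nothing closes it. Limb 2, read as worsening while on drug, is closed.

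**2. How long is the off-drug period that counts?**

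Inputs: the nominal Week 52 visit is Day 364 (52 × 7). The stop weeks are assumed. The cut-off of last dose + 30 days is assumed too, taken from the protocol's safety follow-up length. Last dose day = 7 × stop week.

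| Stop week | Last dose day | Weeks off drug to Week 52 | Days counted now | Days counted with +30 days | Difference |
|---|---|---|---|---|---|
| 4 | 28 | 48 | 364 | 58 | 306 |
| 12 | 84 | 40 | 364 | 114 | 250 |
| 24 | 168 | 28 | 364 | 198 | 166 |
| 36 | 252 | 16 | 364 | 282 | 82 |

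The shorter tables do not remove this. For the Week 12 stop, the 48-week table counts 336 days against 114, a difference of 222. The 24-week table counts 168 against 114, a difference of 54.

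To turn days into the chance of at least one counted event, take a constant rate λ per subject-year, the same on and off drug: P = 1 − exp(−λ × days / 365.25). The values of λ are assumed.

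| λ per year | Current rule, 364 days | Week 4 stop, 58 days | Week 12 stop, 114 days | Week 24 stop, 198 days |
|---|---|---|---|---|
| 0.1 | 9.5% | 1.6% | 3.1% | 5.3% |
| 0.5 | 39.2% | 7.6% | 14.4% | 23.7% |
| 1.0 | 63.1% | 14.7% | 26.8% | 41.8% |

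**3. What does unequal follow-up do to whole-study percentages?**

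Same formula with days = 7 × weeks, comparing 48 with 96 weeks of follow-up (96 is assumed):

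| λ per year | 48 weeks | 96 weeks |
|---|---|---|
| 0.1 | 8.8% | 16.8% |
| 0.5 | 36.9% | 60.1% |
| 1.0 | 60.1% | 84.1% |

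At an unchanged rate, the crude percentage differs through follow-up time alone.

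**The case against.** The strongest reply is that inclusive counting is deliberate and cautious. SAP 9.1.1 leans the same way, and in an uncontrolled study of a drug with a liver signal it is safer to keep late events in the main table. This has weight, and it is why later events should be tabulated rather than dropped. It does not explain why limb 2 stops with treatment while limb 1 does not.

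Several mitigations stand:

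- Only boys who stop drug and remain in the study are affected. Two of eight patients in SMT C11004 discontinued for TEAEs (Protocol 1.3.3), so early stopping is realistic, but that is not a rate for this trial.
- The 24- and 48-week tables largely equalise calendar follow-up, and cohorts are also tabulated separately.
- Treatment-related TEAEs have their own tables, although these rest on open-label attribution and count a missing attribution as related.
- Total TEAE counts and exposure durations are both reported, and listings carry study days. A reader could assemble an approximate rate, but no such summary is planned.

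A reader might go further and infer that biopsy events could put every Cohort 1 and 2 boy in the table against none in Cohort 3. The documents do not support that. A biopsy is a procedure, not an AE, and the second biopsy is optional for boys who terminate early. The line for any TEAE was also near saturation without biopsies in view: all 12 boys in SMT C11003 had a TEAE on every treatment, placebo included, and 7 of 8 did in SMT C11004 (Protocol 1.3.3). SAP 9.4.2 does divide medications into "those taken specifically for the anaesthetics related to the biopsy procedure and all others", but only to produce separate listings. The lack of a matching split for events is not an error.

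Nor is the plan set up to compare cohorts on crude whole-study percentages. The main report takes only SAE data from Cohort 3 (SAP 7.0), and no between-cohort AE comparison is specified.

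**Conclusion.** The point holds within limits. Limb 1 has no end and limb 2 does, so new off-drug events count in a primary endpoint for as long as a boy who has stopped drug is followed. For a Week 12 stop followed to Week 52, that is 364 counted days against 114 with a 30-day cut-off. Over the stop weeks considered, the excess runs from 82 to 306 days per boy. The effect on the tables cannot be sized, because the number of such boys is unknown.

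It would be too strong to say that TEAEs in general have no end date. Worsening is bounded, and boys who complete and leave are bounded by the 30-day follow-up.

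The follow-up criticism applies to the whole-study tables. The shorter tables mostly deal with calendar time, though not with early stopping. The event rates, stop weeks, 96-week follow-up and 30-day cut-off are illustrative assumptions. This is an inexpensive improvement worth making before reporting; it does not invalidate the safety analysis.

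**What to change.** In SAP 5.4.1, apply one window to both limbs: onset or worsening from first dose to last dose + 30 days. That matches the safety follow-up length in Protocol 4.1.1 and the 30-days-from-last-dose period for deaths in Protocol 11.2.2. Tabulate events with later onset separately, so that none are lost.

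In SAP 9.8.1, add exposure-adjusted rates to the whole-study table: subjects with an event and number of events, each per patient-year, with the person-time definition stated to match the counting window.

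A flag for biopsy- or anaesthesia-related TEAEs is an optional extra.

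The cost is a change of SAP wording, one derived flag based on the last dose date that SAP 9.4.1 already uses, one table of later events and a few rate rows. The drawback is that delayed effects with onset more than 30 days after last dose leave the main table, so the later-event table should be presented next to it.

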5.4.2 Laboratory Data

Laboratory parameters will be reported in International System of Units (SI).

Coagulation parameters will only be assessed in Cohorts 2 and 3.

The table below details the times when laboratory measurements will be taken:

| Visit | Cohort | | |
|------------------|---------------|---------------------|---------------------|
| | 1 | 2 | 3 |
| Screening | H, CC, U, LFT | H, CC, U, LFT, Coag | H, CC, U, LFT, Coag |
| Baseline Phase | H, CC, U, LFT | H, CC, U, LFT, Coag | |
| Day 1 | LFT | LFT | H, CC, U, Coag |
| Day 7 | | LFT, Coag | H, CC, U, LFT, Coag |
| Week 4 | LFT | LFT | LFT |
| Week 8 | LFT | LFT | |
| Week 12 | H, CC, U, LFT | H, CC, U, LF, Coag | H, CC, U, LFT, Coag |
| Week 24 | H, CC, U, LFT | H, CC, U, LF, Coag | H, CC, U, LFT, Coag |
| Week 36 | H, CC, U, LFT | H, CC, U, LFT, Coag | H, CC, U, LFT, Coag |
| Week 48 | H, CC, U, LFT | H, CC, U, LFT, Coag | H, CC, U, LFT, Coag |
| Extension Visits | H, CC, U, LFT | H, CC, U, LFT, Coag | H, CC, U, LFT, Coag |

H: Haematology, CC: Clinical Chemistry, U: Urinalysis, LFT: Liver Function Tests, Coag: Coagulation parameters

Changes from baseline will be calculated.

Some laboratory parameters will be categorized to assist identifying values of potential concern. Details are provided in [Section 9.8.3](#).

The following parameters will be assessed relative to the upper limit of normal, e.g. value/ULN:

- Alkaline Phosphatase
- ALT
- AST
- Creatine kinase
- GLDH
- Total Bilirubin

For those parameters recorded as $>x$ or $<x$ a small value (0.01) will be added or subtracted from the value x respectively prior to performing analyses. Listings will present the original value.

5.4.3 Vital Signs

Vital sign measurements will be taken at screening, baseline, end of study, Day 1 and Weeks 12, 24, 36 and 48 during the first 48 weeks and then 3 monthly during the extension phase. If a subject withdraws from the study prematurely they will also be assessed at the termination visit.

Pulse, respiratory rate, oral temperature, and systolic and diastolic blood pressures will be measured.

Changes from baseline will be calculated.

5.4.4 Twelve-Lead Electrocardiogram (ECG)

Triplicate ECG measurements will be taken at screening, baseline, end of study, Day 1 and Weeks 12, 24, 36 and 48 during the first 48 weeks and then 6 monthly during the extension phase. If a subject withdraws from the study prematurely they will also be assessed at the termination visit.

Cohorts 1 and 2

On Day 1 and at Weeks 24 and 48 the measurements will be taken at either pre-AM dose and 0.5, 2, 4 and 6h post-AM dose OR pre-PM dose and 0.5, 2 and 4h post-PM dose. At Weeks 12 and 36 the measurements will be taken at 4h post-AM dose.

Cohort 3

At Weeks 12, 24, 36 and 48 the measurements will be taken at pre-AM dose and 0.5, 2, 4 and 6h post-AM dose.

Extension Phase

At Week 48 (start of extension phase) the measurements will be taken at 0.5, 2, 4 and 6h post-AM dose. Then measurements will be taken at 4h after dosing at each 6 monthly visit.

Heart rate, PR interval, RR interval, QRS complex and QT interval will be recorded. Heart rate corrected QTc will be determined using Fridericia (QTcF) and Bazett (QTcB) formulae.

The average of the triplicate measurements will be used in the summaries of data by visit, however individual replicates and unscheduled data will be used in categorical analyses (e.g. determining number

of subjects with a QTcF \geq 60ms). A categorical analysis will also be conducted based on the averages of the triplicate measurements.

Changes from baseline will be calculated for averaged triplicate data and for individual replicate data.

5.4.5 Echocardiogram (Cohorts 1 and 2)

Echocardiograms will be taken at screening, end of study and Weeks 24 and 48 during the first 48 weeks, and then 6 monthly during the extension phase. If a subject withdraws from the study prematurely they will also have it taken at the termination visit if not performed in the last 12 weeks.

The left ventricular ejection fraction (LVEF), and the fractional shortening (FS) will be recorded. Changes from baseline will be calculated.

Additionally, the site will record if the echocardiogram is normal, abnormal—not clinically significant or abnormal-clinically significant. If abnormal-clinically significant the reason should also be recorded.

5.4.6 Physical Examination

Physical examinations will be conducted at various times during the study. Any clinically significant findings post-dose will be reported as adverse events.

Body weight and height will be measured when physical examinations are conducted. BMI will be derived. Changes from baseline in weight, height and BMI will be calculated.

